The purpose of the study is, using study procedures duplicating in large part those of Garbutt et al (2012), to compare the benefits of 2 treatment arms—high-dose amoxicillin/clavulanate (2000 mg amoxicillin/125 mg po bid) vs regular-dose amoxicillin/clavulanate (875 mg amoxicillin/125 mg po bid)--at day 3 (primary endpoint) and day 10 (secondary endpoint), by reported degree of improvement (primary endpoint, as in Wald et al., 2009) and by SNOT-16 (secondary endpoint, but which was the primary endpoint in Garbutt et al, 2012). We will use amoxicillin/clavulanate, rather than amoxicillin alone, to be in accord with the IDSA 2012 guideline (IDSA, 2012). The duration will be 7 days in line with the IDSA guidelines. We will not have a pure placebo arm since 1) the IDSA guidelines recommend treatment; 2) clinical studies (Wald et al, 1986; Bucher et al., 2003) suggest that treating with the IDSA-recommended regular-dose amoxicillin/clavulanate is equivalent, or almost equivalent, to giving a placebo; 3) we will not exclude patients who we would not want to risk giving a true placebo; and 4) we know that, because of patients' continued belief in the efficacy of antibiotics, recruitment will be easily in a study with two treatment arms, rather than treatment and placebo arms. In addition, we will study whether the response to antibiotics can be predicted by the presence or not of penicillin-resistant S. pneumoniae in the nasopharynx.

Thus the study questions are: 1. Is high-dose amoxicillin/clavulanate superior to regulardose in improving the clinical symptoms of presumed sinusitis? 2. Does the higher dose result in increased incidence and/or severity of adverse effects, such as diarrhea? 3. Does the resistance pattern of S. pneumonia in nasopharyngeal cultures predict response to antibiotic treatment? The hypotheses are yes for #1, no for #2, and no for #3 (but with the expectation of insufficient power to answer question #3).

B. Study Design

Study type: randomized, double-blind clinical study with two active treatment arms

Location: AMC Internal Medicine and Pediatrics office in Latham, NY

Duration: 2 years; each participant will be in the study for 30 days.

Subjects:

Inclusion criteria

1. Adults age 18 and over. The study on children already indicates a benefit of high-dose amoxicillin-clavulanate over placebo. The restriction to adults eliminates the need for parental consent.

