6. Drop outs:

- a. The participant can exit the study at any time, if much sicker, by going to the emergency department
- b. The participant can request, at any time, treatment with open-label antibiotic, e.g. doxycycline or levofloxacin (recommended by the IDSA), at the discretion of the clinician in the office or on call.
- c. The participant will be formally given this option at the day 3 telephone call.
- 7. Participants will be asked additionally at day 10
 - a. To guess which treatment they took (to evaluate adequacy of blinding, although it is expected that patients who get better faster will assume they took the higher dose).
 - b. To indicate how many doses they took. We will not ask for the bottles to be returned (which would require an otherwise unnecessary office visit for the participants).
 - c. To indicate if they would take that particular medication again if prescribed.
- 8. Participants will be asked additionally at day 30 if, and to what extent, they had persistence, resolution, or recurrence of symptoms.

Measurements (bacteriological)

Nasal cultures (anterior) will be performed on every patient. The cultures will be processed at the Albany Medical Center microbiology laboratory to assess:

- 1. What pathogens are present?
- 2. If S. pneumonia, what is its level of penicillin resistance?
- 3. If S. aureus, is it methicillin resistant?

Endpoints

- 1. Primary endpoint: Major mprovement of subjective symptoms at day 3 (i.e., 48-72 hours after starting treatment), rated as "a lot better" or "no symptoms."
- 2. Secondary clinical endpoints:
 - a. At least mild improvement in subjective symptoms at day 3: percent in each group rating their condition as "a little better," "a lot better," or "no symptoms"
 - b. Improvement in SNOT-16 score at day 3. Garbutt et al. (2012) indicate that a minimally important difference is 0.5 (on a scale of 0-3), although they used an effect size of 0.25 for their study size determination (requiring a bigger sample size). We will compare the percent in each group with average improvement \geq 0.5
 - c. The same comparisons at days 10 and 30 (one month).
 - d. Comparisons of side effects—diarrhea and others mentioned by participants on scale of 0=none to 3=severe--at days 3 and 10.
 - e. Percent of who dropped out because of side effects or inefficacy (switched to alternative antibiotic or went to the ED).

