 - a. To have the patient remain in the study, after reassurance and/or advice on treating side effects;
 - b. To switch the patient to a different antibiotic because of apparent inefficacy or bad side effects (and drop her out of active part of study):
 - c. To bring the patient into the office to be seen (and decide then if the patient will stay in or drop out of the study); or
 - d. To send the patient to the ED (if quite ill) (and drop her out of the active part of the study).
- 20. If the participant drops out, the clinician can ask the pharmacists to look up the results of the culture (if done) to help guide further management. In practice, this is highly unlikely

- since the patient who fails the study medication will be switched to another antibiotic (generally doxycycline or levofloxacin).
- 21. If a patient drops out, the clinician involved will fill out the Drop-Out form.
- 22. The participant who drops out of the active part of the study will still be called at 3, 10, and 30 days, if he or she agrees (to enable an intention to treat analysis with maximum data).
- 23. Culture results, identified only by the participant's study number, will be collected by the pharmacist and kept separately. The results will be entered onto the Data Collection Form and the data base only at the end of the study, i.e. will not be known to the residents and students as they make phone calls. The pharmacist will tell a clinician the results for a particular patient only if the patient drops out and knowledge of the culture result might help in further management.
- 24. At the end of the study, the Data Collection Forms for each participant will be scanned into the EHR (so that the data will be clinically useful for the patient) and then destroyed (along with the Day 0 SNOT-16 form).

Costs

1. Medication

- a. Amox-clav 1000/62.5 two tabs bid x 7 days = \$72.36 per patient. Total for 150 patents \$10,854. We will try to get the antibiotic from 2 different generic manufacturers so that the 2 tabs look slightly different. Thus the total cost may be higher, but unlikely more than \$12,000.
- b. Amox-clav 875/125 t tab bid x 7 days = \$7.00 per patient. Total for 150 patients \$1,050.
- c. Placebo. We are still trying to find information on costs, but doubt it will cost more than \$5 per pill. Total for 150 patients \$750 (or less).
- d. Packaging. Each patient will need 2 bottles and labels, likely \$1 per patient. Total for 300 patients of \$300.

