How are your sinus symptoms (scale of 1 to 6)? (circle one) 1 a lot worse, 2 a little worse, 3 the same, 4 a little better, 5 a lot better, or 6 no symptoms

SNOT-16

Rate how much you have been bothered, in terms of severity and frequency, by the following symptoms on a scale of 0=no problem, 1=mild or slight problem, 2=moderate problem, or 3=severe problem

- 1. Need to blow nose:
- 2. Sneezing:
- 3. Runny nose:
- 4. Cough:
- 5. Postnasal discharge:
- 6. Thick nasal discharge:
- 7. Ear fullness:
- 8. Headache:
- 9. Facial pain or pressure:
- 10. Wake up at night:
- 11. Lack of a good night's sleep:
- 12. Wake up tired:
- 13. Fatigue:
- 14. Reduced productivity:
- 15. Reduced concentration:
- 16. Frustrated, restless, or irritable:

Do you have any side effects? (circle or check)

- 1. Diarrhea: 0 none, 1 mild, 2 moderate, 3 severe
- 2. Abdominal pain: 0 none, 1 mild, 2 moderate, 3 severe
- 3. (For women) vaginal discharge and itching: 0 none, 1 mild, 2 moderate, 3 severe
- 4. Rash: [] rash without itching [] rash with itching (or hives)
- 5. Other:

E. DATA COLLECTION FORM

See attached. (Each day—enrollment, day 3, day 10, and day 30--will be on a separate sheet of paper.)

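### Side effects at day 10 cannot be dated to before or after a switch to open-label antibiotic, which can bias the dose comparison in endpoint 2d if switching differs by arm

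*Combined protocol and SAP*

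**What the plan says.** All references are to the combined protocol and SAP.

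- **Question.** Study question 2 (Purpose of Current Study) is about dose: "Does the higher dose result in increased incidence and/or severity of adverse effects, such as diarrhea". The stated hypothesis is that it does not.
- **Endpoint.** Section B, Endpoints, item 2d compares by arm diarrhea and "others mentioned by participants on scale of 0=none to 3=severe--at days 3 and 10". It has no rule for participants who have changed antibiotic. Section D leaves the secondary analyses to the statistician.
- **Switching.** Measurements (clinical), item 6: "The participant can request, at any time, treatment with open-label antibiotic, e.g. doxycycline or levofloxacin", and "The participant will be formally given this option at the day 3 telephone call". Follow-up item 19 gives the clinician the choice "To switch the patient to a different antibiotic because of apparent inefficacy or bad side effects". Item 20 says that knowledge of the culture is unlikely to be needed "since the patient who fails the study medication will be switched to another antibiotic", generally doxycycline or levofloxacin.
- **Follow-up after a switch.** Follow-up item 22: "The participant who drops out of the active part of the study will still be called at 3, 10, and 30 days", provided the participant agrees. The stated aim is an intention-to-treat analysis.
- **What is recorded.** Measurements (clinical), item 5, lists side effects and severity at days 3 and 10. Item 7 adds, at day 10, the treatment guess, the number of doses taken and willingness to take the drug again. The questionnaire text shown near the end of the document asks "Do you have any side effects? (circle or check" and then lists symptoms with grades. None of these asks for an onset date or the drug in use.

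**The concern.** The formal offer to switch comes at day 3, so most open-label exposure would fall between the two side-effect assessments. Take a participant who changes drug after the day-3 call and develops diarrhea on the second antibiotic. At day 10 that person reports diarrhea, is analysed under the randomised arm, and the listed data do not show which drug preceded the symptom. Reported doses taken give exposure to study drug but not onset. If onset is not collected during the trial, the statistician cannot recover it afterwards.

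Timing may add to this. Study drug lasts 7 days, so a participant who completes it has been off it for about three days at the day-10 call. Someone who switched may still be taking the second antibiotic, whose duration is not stated.

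The stake is study question 2. If the high dose works better, more regular-dose participants are likely to switch for inefficacy. Side effects of the second drug are then added mainly to the regular-dose arm, which would mask a true dose-related increase and favour the plan's own hypothesis. If switching is driven instead by side effects in the high-dose arm, the bias runs the other way.

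**Working it through.** **The plan's own figures.** No figure is stated for the side-effect comparison. The one calculated figure nearby is the primary-endpoint sample size, and it reproduces: (1.96 + 0.842)² × (0.34×0.66 + 0.50×0.50) / 0.16² = 145.4, so 146 per arm. This point does not affect it.

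**Inputs from the documents.** Diarrhea 16.7% high dose and 14.4% standard dose, difference 2.3 points (section E, from the adult bronchitis study). Withdrawal for adverse effects 2.3% high and 4.0% standard (same source). Major improvement at day 3 assumed at 34% versus 50% (Sample size determination). Planned size 150 per arm.

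**Assumptions.** The documents give neither the share *s* who switch in each arm nor the chance *q* that a switcher without diarrhea gets it on the new drug. Both are varied below.

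**Formula.** Observed rate = p + (1 − p) × s × q, where p is the rate due to study drug.

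Worked case, s = 15% regular and 8% high:
- q = 15%: regular gains 0.15×0.856×0.15 = 1.93 points; high gains 0.08×0.833×0.15 = 1.00. Shift 0.93; the difference falls from 2.3 to 1.4.
- q = 30%: gains 3.85 and 2.00. Shift 1.85; the difference falls to 0.4.

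Other cases:

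| Switching, high vs regular | q | Apparent difference (points) | Shrinkage (points) |
|---|---|---|---|
| 20% vs 20% | 20% | 2.2 | 0.1 |
| 2.3% vs 4.0% (cited withdrawals only) | 15% to 30% | 2.1 to 1.8 | 0.2 to 0.5 |
| 10% vs 20% | 5% | 1.9 | 0.4 |
| 10% vs 20% | 10% | 1.4 | 0.9 |
| 10% vs 20% | 20% | 0.5 | 1.8 |
| 10% vs 30% | 20% | −1.2 | 3.5 |

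**A case tied to the plan's effect assumption.** Under 34% versus 50%, the shares without major improvement at day 3 are 66% regular and 50% high. Suppose the same fraction f of them switches in each arm. The shift is then q × f × (0.66×0.856 − 0.50×0.833) = q × f × 0.148. For f from 10% to 30% and q from 15% to 30%, this is 0.2 to 1.3 points. The switching ratio here is 66/50 = 1.3, less uneven than in the worked case (15/8 = 1.9).

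**Sampling error.** SE = √[(0.144×0.856 + 0.167×0.833)/150] = 4.2 points, so the 95% interval is about ±8 points. Power to detect 2.3 points is about 8%.

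**Cost of counting only pre-switch side effects.** With 15% versus 8% switching at day 3, and half of diarrhea assumed to begin later, the regular arm loses 0.15×0.144×0.5 = 1.1 points and the high arm 0.08×0.167×0.5 = 0.7. The apparent difference widens by 0.4 point.

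**The case against.** **The plan does not state the rule.** A reader might infer that the plan decides to count second-antibiotic side effects against the randomised dose. It does not say so. That switchers enter endpoint 2d follows from item 22 and the absence of any exclusion; it covers only those who agree to further calls, and secondary analyses are left open. This stands, and the point is therefore worded as what the text implies.

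**The relevant forms are not visible.** The questionnaire shown lacks the extra day-10 items, so it is probably the day-3 sheet given to patients (Enrollment item 13). The day-10 sheet and the Drop-Out form (Follow-up item 21) cannot be seen and may hold a switch date or more. This also stands. However, the listed measurements, including the day-10 additions, contain no onset item, and no analysis rule in the text would use one.

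**Other parts of the plan serve the question.** The day-3 comparison precedes or coincides with the formal offer, and endpoint 2e counts drop-outs for side effects or inefficacy. Both are largely untouched, but neither dates side effects that appear between days 3 and 10.

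**Comparison by randomised arm is legitimate.** A reader might infer that the day-10 result is worthless as a comparison of arms. It remains a valid treatment-policy comparison, and with equal switching the difference hardly moves. What it does not isolate is the effect of dose, which is what study question 2 asks about.

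**The bias is small beside the noise.** Correct under most of the assumptions above. That lowers the priority but does not remove the reason for a cheap change.

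**Conclusion.** The point holds as a gap in data collection and reporting for one secondary endpoint. As the text reads, switchers who agree to further calls stay under their randomised arm, and nothing listed separates side effects that began before the switch from those that began after it. The day-10 part of endpoint 2d can then be biased if switching differs by arm, probably toward the hypothesised absence of an increase.

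The size is unknown. It is about 0.2 to 2 points under moderate assumed rates, near zero with equal switching, and larger (3.5 points, with the sign reversed) only under a 20-point gap in switching with q = 20%. Every switching and post-switch rate is an assumption, except the cited withdrawal rates, which come from another indication and leave out switches for inefficacy. The documents do not support a claim that the trial's conclusion on side effects would usually change, since the interval is about ±8 points. The day-3 comparison, endpoint 2e, the primary endpoint and the sample size are largely unaffected. This is a cheap improvement worth making before enrolment.

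**What to change.** First check the Drop-Out form and the day-10 sheet. Unless they already do so:

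1. On the Drop-Out form, record the date of the last study dose, the start date of the new antibiotic, and the grade of each listed side effect up to that point.
2. On the day-10 sheet, ask participants who switched whether each side effect began before or after the new antibiotic.
3. In endpoint 2d, report two comparisons by randomised arm with all participants in the denominator: side effects with onset before any other antibiotic, keeping those that led to the switch; and the all-data day-10 comparison.
4. Report time on study drug by arm and read the two comparisons together. The pre-switch comparison gives less time at risk to the arm that switches more, so neither should be read alone.

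The cost is a few lines on two forms and a short addition to endpoint 2d. No treatment decision, visit or sample size changes. The onset information has to be collected as the trial runs.

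### Secondary endpoint 2e pools exits for side effects with exits for inefficacy and does not count patients who stop the tablets for side effects without contacting a clinician

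*Combined protocol and SAP*

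**What the plan says.** In the combined protocol and SAP, section B (Study Design), Endpoints, item 2e is one percentage: "Percent of who dropped out because of side effects or inefficacy (switched to alternative antibiotic or went to the ED". The bracket names two routes only.

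The routes out of the study appear in two places:

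- Measurements (clinical), item 6a: "The participant can exit the study at any time, if much sicker, by going to the emergency department". Item 6b: "The participant can request, at any time, treatment with open-label antibiotic". Item 6c offers this option formally at the day-3 call.
- Procedure, Follow-up, item 19b: "To switch the patient to a different antibiotic because of apparent inefficacy or bad side effects (and drop her out of active part of study". Item 19d is referral to the ED. Item 19c brings the patient into the office, where staying in or dropping out is decided. Item 19a keeps the patient in the study with reassurance or advice on side effects.

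On recording, Follow-up item 21 says: "If a patient drops out, the clinician involved will fill out the Drop-Out form". Measurements item 7b asks participants at day 10 "To indicate how many doses they took", with no bottle return.

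The Purpose section lists benefit as study question 1 and harm as question 2: "Does the higher dose result in increased incidence and/or severity of adverse effects, such as diarrhea". The hypothesis for question 2 is no. Endpoint 2d compares graded side effects at days 3 and 10. Section D leaves the analysis of secondary outcomes to the statistician.

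**The concern.** There are two separate problems with 2e.

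**Pooling.** The two reasons for leaving belong to different study questions. A difference in the pooled percentage would not show whether the dose worked better or was harder to take, and a null result would not show that neither happened. Section E (Risks) quotes withdrawals for adverse effects alone from the cited bronchitis trial. As worded, 2e would not yield the matching figure for this trial.

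**Capture.** Treatment lasts 7 days and the calls fall on days 3 and 10. A patient who stops on, say, day 4 because of diarrhoea and tells nobody has not switched antibiotic, visited the ED or come to the office. No clinician is involved, so no Drop-Out form is triggered. The dose count at day 10 would show the shortfall, but no listed endpoint uses it, and the text reviewed does not ask why doses were missed.

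If the higher dose did cause more such stops, leaving them out would pull the observed difference towards zero, which is also the plan's hypothesis for question 2.

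**Working it through.** **The plan's own figure.** The plan gives no rate, sample size or power for 2e. Its sample size for the primary endpoint reproduces: (1.960 + 0.842)² × [0.34×0.66 + 0.50×0.50] / 0.16² = 7.849 × 0.4744 / 0.0256 = 145.4, so 146 per group. The points below use the planned 150 per group and do not otherwise depend on that calculation.

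**Which exits does the text catch?**

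| Situation | Covered by | Named in the 2e bracket? |
|---|---|---|
| Switch to another antibiotic | 6b, 19b | Yes |
| ED visit | 6a, 19d | Yes |
| Drop-out decided at an office visit | 19c | No |
| Stops tablets, contacts nobody | none; visible only in the day-10 dose count (7b) | No |

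**Method for the power figures.** Power = Φ[(d − 1.96·SE0)/SE1], with d = |p1 − p2|, SE0 = √(2·p̄(1−p̄)/150) and SE1 = √[(p1(1−p1) + p2(1−p2))/150], two-sided alpha 0.05.

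**Pooling (all rates assumed; regular vs high dose).**

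| Side effects | Inefficacy | Pooled | Power: side effects | Power: inefficacy | Power: pooled |
|---|---|---|---|---|---|
| 4% vs 8% | 10% vs 6% | 14% vs 14% | 31% | 25% | 5% (no difference) |
| 4% vs 12% | 15% vs 7% | 19% vs 19% | 73% | 60% | 5% (no difference) |
| 4% vs 12% | 10% vs 8% | 14% vs 20% | 73% | 9% | 28% |

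Worked case, 4% vs 12%: p̄ = 0.08, SE0 = 0.03133, SE1 = 0.03098, so Φ[(0.08 − 0.06140)/0.03098] = Φ(0.600) = 0.73.

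The same in counts, again assumed: inefficacy 12 vs 3 gives p = 0.017, side effects 4 vs 12 gives p = 0.040, and pooled 16 vs 15 gives p = 0.85 (uncorrected tests of two proportions). The side-effect result is fragile: Fisher's exact test gives p = 0.069, and 4 vs 11 gives p = 0.064 even uncorrected.

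**Capture (assumed true stopping for side effects 4% vs 12%).** If a share c of stoppers is counted, the observed difference is 8c percentage points.

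| Share counted | Observed rates | Difference (points) | Power |
|---|---|---|---|
| 100% | 4% vs 12% | 8 | 73% |
| 75% | 3% vs 9% | 6 | 59% |
| 50% | 2% vs 6% | 4 | 42% |
| 25% | 1% vs 3% | 2 | 23% |

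**At the documents' own rates.** Section E cites withdrawals for adverse effects of 2.3% at high dose and 4.0% at standard dose. Expected counts are 150 × 0.023 = 3.45 and 150 × 0.040 = 6.0. Power is 13%, and 1,656 per arm would be needed for 80%. With counts this small, three uncounted stoppers in the high-dose arm would separate a true 6 vs 6 from an observed 3 vs 6.

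**The case against.** The strongest case on the other side has five parts.

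1. **Harm is measured elsewhere.** Endpoint 2d grades side effects by arm at days 3 and 10, and item 7c asks whether patients would take the medication again. Drop-outs are still called if they agree. A patient who stopped on day 4 for diarrhoea can report it at day 10. This stands. A reader might infer that a null 2e would hide the harm of the higher dose altogether; the documents do not support that. What 2d does not show is whether patients stayed on treatment.

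2. **Not every drop-out needs a switch or an ED visit.** A reader might infer that it does, but item 19c allows a drop-out decision at an office visit. That stands too. The route still requires contact with a clinician, and 2e does not name it. The bracket could also be read as qualifying inefficacy only. Side-effect exits would then have no stated route, and the pooling would remain.

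3. **The cited data point the other way.** Withdrawals for adverse effects were lower at high dose, as was any adverse effect (36.6% vs 42.4%). Diarrhoea was only slightly higher (16.7% vs 14.4%, p = 0.36), and the plan notes that clavulanate, which it holds mainly responsible, is at equal dose in both arms. So cancellation cannot be called the expected result. If the cited direction held, 2e would merge a tolerability gain with any efficacy gain, and the figure would still not be interpretable for either question.

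4. **The illustrations are built to cancel, and power is low.** True. They show the mechanism, not a forecast. The case rests on interpretability and capture, not on significance.

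5. **The Drop-Out form may already record the reason, and the statistician may split by it.** The form is not in the text reviewed, so this cannot be checked, and nothing forbids a split. But the plan does not commit to one, and the form is not triggered for a patient who stops unannounced.

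**Conclusion.** The point holds for endpoint 2e. The pooled percentage cannot be read for benefit or for harm, and patients who stop for side effects without contacting a clinician are not counted in it. What is blurred or under-counted is discontinuation because of side effects, not tolerability as a whole.

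The size cannot be fixed from the documents. Under assumed opposite effects of 8 points each, the pooled difference is exactly zero. Counting half of the stoppers halves an 8-point difference and cuts power from 73% to 42%. At the cited rates only about 3 to 6 side-effect withdrawals per arm are expected.

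The capture gap assumes that neither the Drop-Out form nor the day-10 form already asks why tablets were stopped; the text reviewed does not settle this. The matter is secondary and leaves the primary analysis and sample size untouched. It is still worth correcting before enrolment, because a reason not asked at day 10 cannot be recovered reliably later.

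**What to change.** Replace 2e with two figures, each reported by arm:

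- (i) exit for inefficacy;
- (ii) permanent early stop of study tablets for side effects, whether or not another antibiotic was started or the ED was visited.

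Identify (ii) from the Drop-Out form together with the day-10 dose count. The full course is 2 doses a day × 7 days = 14 doses, so when a participant reports fewer than 14, ask the reason at the same call. Confirm that the Drop-Out form records the reason, including for decisions made under item 19c. Keep the pooled percentage as a description.

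The cost is one endpoint sentence and one question at a call already planned, with no new visit. The downside is one extra secondary comparison with few events, which should be presented as descriptive.
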